**Table 16. Case Definition for IRRs – IV Study Drugs Administered Alone Or In Combination With Non-IV Study Drugs**

Condition	Selection criterion
If AE meets [1 AND 2] OR [3 AND (4A OR 4B)] then AE is classified as an IRR	
1	PT is included in the ‘IRRs SIGNS and SYMPTOMS’ list
2	
 
• AE onset date = date of infusion of study drug AND
 
• AE timing related to study drug (‘DURING’, ‘AFTER’) AND
 
• AE outcome in (‘RECOVERED/RESOLVED’, ‘RECOVERED/RESOLVED WITH SEQUELAE’, ‘RECOVERING/RESOLVING’) AND
 
• AE end date – AE onset date <math>\leq 2</math>
 

3	PT is included in the ‘IRRs CORE’ list
4A	
 
• AE onset date = date of infusion of study drug AND
 
• AE timing related to study drug in (‘DURING’, ‘AFTER’)
 

4B	AE onset on the day after infusion

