#### **6.6.1. Adverse events**

Treatment-emergent adverse events (TEAEs) are those events with onset dates occurring during the on-treatment period as defined in Section 3.5.1.

All analyses described will be based on TEAEs (started during the on-treatment period) if not otherwise specified. The AE listings will include all AEs (whether treatment-emergent or not). AEs outside the on-treatment period will be flagged in the listings.

- **Related Adverse Events:** adverse events with relationship to study treatment (as recorded on the AE eCRF page, Relationship with study treatment = Related) reported by the investigator and those of unknown relationship (ie, no answer to the question 'Relationship with study treatment'). Related AEs are those related to any study drug (ie, at least one of the study drugs).
- **Serious Adverse Events (SAE):** serious adverse events (as recorded on the AE eCRF page, Serious Adverse Event = Yes).
- **Adverse Events Leading to Interruption of Study Treatment:** adverse events leading to interruption of study treatment (as recorded on the AE eCRF page, Action taken with study treatment = Drug interrupted). The eCRF does not allow for a clear separation between interruption of an infusion and delays of administration for a parenteral drug as

both are recorded using the same term on the eCRF (“Drug interrupted”). IRRs will be excluded in the analysis of AEs leading to Drug Interruption in case they only led to an interruption of the infusion.

- **Adverse Events Leading to Permanent Treatment Discontinuation:** adverse events leading to permanent discontinuation of study treatment (as recorded on the AE eCRF page, Action taken with study treatment = Drug withdrawn).
- **Adverse Events Leading to Death:** adverse event leading to death (as recorded on the AE eCRF page, Outcome = Fatal, as well as AEs of Grade 5).
- **Immune-related Adverse Events (irAE):** irAEs (as identified according to the methodology outlined in Appendix 1 for a pre-specified search list of MedDRA PTs, documented in the Safety Review Plan (SRP) and finalized for analysis of the current study data prior to DB lock)
- **Infusion-related Reactions (IRR):** IRRs (as identified according to the methodology outlined in Appendix 2 for a pre-specified search list of MedDRA PTs documented in the SRP and finalized for analysis of the current study data prior to DB lock).

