5	
A) No clear etiology (other than immune mediated etiology)
 
B) Histopathology / biopsy consistent with immune-mediated event
 
Event is in if          [Answer to 5B1 and 5B2 is YES (regardless of answer to 5A)]          OR          [Answer to 5B1 is YES AND answer to 5B2 is NO AND answer to 5A is NO]          OR          [Answer to 5B1 is NO AND answer to 5A is NO]
	
A) From the AE eCRF page.          Is the AE clearly related to an etiology other than immune-mediated etiology? Yes / No          If answer is Yes, check all that apply:
 
 
• Underlying malignancy / progressive disease.
 
• Other medical conditions.
 
• Prior or concomitant medications / procedures.
 
• Other. Specify.
 
 
B) From the AE eCRF page.          B1) Was there a pathology /histology evaluation performed to investigate the AE? Y/N          B2) If answer to the above is Yes, does the pathology/histology evaluation confirms an immune mediated mechanism for the AE? Y/N          B3) If pathology / histology evaluation performed to investigate the AE, provide summary of relevant findings of the pathology /histology report. (Free Text)

---	---	--

The data set associated with irAEs may be refined based on medical review. The final data set including any changes based on medical review (eg, addition of cases that are not selected by the programmatic algorithm) will be the basis of the irAE analyses.

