## Appendix 2. Infusion Related Reactions

For defining an AE as IRR, the onset of the event in relation to the infusion of study drug and time to resolution of the event will be considered.

- All AEs identified by the MedDRA PT query describing signs and symptoms will be considered potential IRRs when onset is on the day of study drug infusion (during or after infusion) and the event resolved with end date within 2 days after onset.
- All AEs identified by the MedDRA PTs of Infusion related reaction, Drug hypersensitivity, Anaphylactic reaction, Hypersensitivity, Type 1 hypersensitivity, will be considered potential IRRs when onset is on the day of study drug infusion (during or after the infusion) or the day after the study drug infusion (irrespective of resolution date).

The list of MedDRA PTs for ‘IRRs SIGNS and SYMPTOMS’ and PTs ‘IRRs CORE’ are defined in the SRP for avelumab.

Infusion-related reactions (IRRs) will be programmatically identified as outlined in Table 16 or Table 17 and will be identified for IV drugs only.

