**Table 17. Case Definition for IRRs – IV Study Drugs Administered in Combination (eg, Doublets or Triplets)**

Condition	Selection criterion
	
IRR can be associated with the first IV drug and/or subsequent IV drugs that are administered in combination. Without loss of generality assume triplet IV with D1 administered first then D2 then D3. The IV study drug or drugs associated with the IRR need to be identified in the analysis data set to enable subsequent analysis.
 
The following are not sequential and an AE can be classified as an IRR associated with multiple DJ from one or more of I, II, III, IV, V below:
 
I - If the AE meets [1 AND 2A1] for a DJ then the AE is classified as an IRR associated with the DJ that meets the 2A1 criterion
 
II - If the AE meets [1 AND 2A2] for a DJ then the AE is classified as an IRR associated with the DJ and associated with DJ+1 that meets the 2A2 criterion
 
III - If the AE meets [3 AND 4B] for any DJ then the AE is classified as an IRR associated with all DJ that meet the 4B criterion.
 
IV- If the AE meets [3 AND 4A1] for a DJ then the AE is classified as an IRR associated with the DJ that meets the 4A1 criterion
 
V- If the AE meets [3 AND 4A2] for a DJ then the AE is classified as an IRR associated with the DJ and associated with DJ+1 that meets the 4A2 criterion

1	PT is included in the ‘IRRs SIGNS and SYMPTOMS’ list
2A1	
 
• AE onset date = date of infusion of study drug DJ AND
 
• AE timing related to study drug DJ (‘DURING’, ‘AFTER’) AND
 
• [AE timing related to study drug DJ+1 (‘BEFORE’) OR AE onset date < date of infusion of study drug DJ+1] AND
 
• AE outcome in (‘RECOVERED/RESOLVED’, ‘RECOVERED/RESOLVED WITH SEQUELAE’, ‘RECOVERING/RESOLVING’) AND
 
• AE end date – AE onset date ≤ 2
 

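### A fatal infusion-day event coded only to a sign-or-symptom term can never be counted as an infusion-related reaction, and Appendix 2 gives no medical-review route to add it

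*SAP*

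**What the plan says.** Section 3.5.1 of the SAP names IRRs as adverse events of special interest. Section 6.6.1 defines them as "IRRs (as identified according to the methodology outlined in Appendix 2 for a pre-specified search list of MedDRA PTs documented in the SRP", so the method is in Appendix 2 and the Safety Review Plan (SRP) supplies the term list.

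Appendix 2 sets up two tiers.

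- **Sign-or-symptom terms.** Onset must be on the infusion day, during or after the infusion, and the text requires that "the event resolved with end date within 2 days after onset". Table 16, condition 2, implements this as "AE outcome in (‘RECOVERED/RESOLVED’, ‘RECOVERED/RESOLVED WITH SEQUELAE’, ‘RECOVERING/RESOLVING", joined by AND to the timing criteria and a limit of 2 days from onset to end. Table 17, conditions 2A1 and 2A2, repeats the outcome list and the limit "AE end date – AE onset date ≤ 2".
- **Core terms** (such as infusion related reaction or anaphylactic reaction). Onset may be on the infusion day "or the day after the study drug infusion (irrespective of resolution date"), and no outcome is required.

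Section 6.6.1 treats an event as leading to death when it has "Outcome = Fatal, as well as AEs of Grade 5", so Fatal is a separate recorded outcome. For immune-related events, Appendix 1 adds: "The data set associated with irAEs may be refined based on medical review", including the "addition of cases that are not selected by the programmatic algorithm". Appendix 2 contains no corresponding sentence.

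**The concern.** The outcome criterion is meant to keep transient symptoms and drop persistent ones. As written it also drops the most severe case: a symptom that begins during an infusion and ends in death shortly afterwards. Because IRR status is assigned by program and no review step is stated, nothing in the SAP restores the event.

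Section 6.6.4 tabulates IRRs by preferred term and maximum grade, and serious IRRs by preferred term. It has no separate table of fatal IRRs, so the maximum-grade table is where a Grade 5 reaction should be visible. For sign-or-symptom terms, a zero there would reflect the definition and not what was observed. The event would also be missing from the IRR row of the overall summary in Section 6.6.1.1. For this class of event the error can only understate severity.

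**Working it through.** The SAP gives no figure to reproduce. The check is of the classification logic.

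**Step 1: the rules.** Table 16 classifies an event as an IRR if [1 AND 2] OR [3 AND (4A OR 4B)]. Table 17 uses [1 AND 2A1], [1 AND 2A2], [3 AND 4A1], [3 AND 4A2] and [3 AND 4B]. Condition 1 is membership of the sign-or-symptom list; condition 3 is membership of the core list.

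**Step 2: an event on the sign-or-symptom list only, outcome Fatal.**
- Condition 3 is false, so every core route is false.
- Conditions 2, 2A1 and 2A2 each require one of three recovered or recovering outcomes. Fatal is not one of them, so all three are false whatever the timing or duration.
- Every stated route is false.

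**Step 3: enumeration.** Infusion-day events were run through both tables for durations of 0, 1, 2 and 3 days. For Table 16, timing relative to the drug was before, during or after: 3 × 4 = 12 combinations. For Table 17, timing varied for both the drug and the next drug: 3 × 3 × 4 = 36 combinations.

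| Event | Table 16 | Table 17 |
|---|---|---|
| Sign-or-symptom list only, recovered or recovering | 6 of 12 | 18 of 36 |
| Sign-or-symptom list only, Fatal | 0 of 12 | 0 of 36 |
| Also on core list, Fatal | 8 of 12 | 24 of 36 |

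The recovered counts follow directly: 2 eligible timings × 3 eligible durations = 6, and 2 × 3 × 3 = 18. With a core term the duration limit falls away: 2 × 4 = 8, and 2 × 3 × 4 = 24. Between the first two rows only the outcome changes, so the outcome criterion alone removes the fatal event. The third row shows that the gap is confined to terms outside the core list.

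**Step 4: is there another route?** Section 6.6.1 points to Appendix 2 for the method and to the SRP for the terms. The review provision in Appendix 1 refers to the immune-related data set only. No other section extends it to IRRs.

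**Step 5: size.** The SAP gives no frequency. Assume 0 or 1 such event in a cohort. Using planned sizes from Sections 2.2.1 and 5.1.1, one event is 1/20 = 5.0%, 1/25 = 4.0%, 1/28 = 3.6% or 1/35 = 2.9%. The IRR tables show no fatal event for these terms in either case.

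**The case against.** The best defence is that the two tiers are deliberate. Non-specific symptoms in patients with advanced cancer are often due to the disease, and requiring quick resolution separates a transient reaction from progression. Text and tables agree, so there is no contradiction. A severe reaction may well be coded to a core term. The death would not be hidden: if treatment-emergent it appears among events leading to death (Section 6.6.1.1) and, if recorded as serious, in the serious-event tables (Section 6.6.3). Section 6.6.2 tabulates the reason for death, including treatment toxicity, and lists the death with dosing dates and a 30-day flag. Immune-related events also call for more judgement on etiology than IRRs do, which may explain why only Appendix 1 provides for review.

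Most of this stands as a limit on the impact. It does not close the gap. Filtering out persistent symptoms does not require dropping an event that ended in death within 2 days. The sign-or-symptom route exists because reactions may be recorded as individual symptoms, so coding to a core term cannot be relied on. The other outputs show the death but do not label it as an infusion reaction.

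Two further points are fair. The sign-or-symptom rule has no causality test, so the overall IRR rate may also be inflated by unrelated symptoms; the one-way understatement applies only to the fatal subset. Events recorded as not recovered or with unknown outcome (labels assumed here) are excluded as well, but for an event that has not ended this is consistent with the filter for transient symptoms.

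**Conclusion.** The point holds. Under both tables, an infusion-day event coded only to a sign-or-symptom term with outcome Fatal cannot be classified as an IRR, and the SAP states no way to add it. This is a badly fixed definition of an adverse event of special interest, with limited consequences: the outputs are descriptive, no hypothesis test or dose-limiting toxicity rule uses them, and the deaths are reported elsewhere. The change is worth making because it is cheap and because a fatal count in this table should come from the data.

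The conclusion on the logic needs no assumption beyond the SAP text. The size rests on the assumed 0 or 1 event per cohort. Which terms are affected is unknown, because the lists are in the SRP, which is not at hand.

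**What to change.** 1. Keep the outcome criterion and the 2-day limit in conditions 2, 2A1 and 2A2 for automatic classification.
2. Flag for medical review, without automatic inclusion, any sign-or-symptom event with onset during or after infusion on the infusion day, outcome Fatal and death within 2 days of onset.
3. Add to Appendix 2 the two closing sentences of Appendix 1, with IRRs in place of irAEs, so that review may add cases the program does not select and the reviewed data set is the basis of the IRR analyses.

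A minor case can use the same review: a recovered infusion-day event whose missing stop day was imputed to the month end under Section 5.3.2.2 and which fails the 2-day limit only for that reason.

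The cost is two sentences and one flag, built from the death date already used in Section 6.6.2, plus review of a small number of events. The drawback is some judgement, in an open-label study, in separating disease deaths from reactions. Decisions should be documented before database lock, when the term list is also finalized.

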**Table 17. Case Definition for IRRs – IV Study Drugs Administered in Combination (eg, Doublets or Triplets)**

Condition	Selection criterion
	
IRR can be associated with the first IV drug and/or subsequent IV drugs that are administered in combination. Without loss of generality assume triplet IV with D1 administered first then D2 then D3. The IV study drug or drugs associated with the IRR need to be identified in the analysis data set to enable subsequent analysis.
 
The following are not sequential and an AE can be classified as an IRR associated with multiple DJ from one or more of I, II, III, IV, V below:
 
I - If the AE meets [1 AND 2A1] for a DJ then the AE is classified as an IRR associated with the DJ that meets the 2A1 criterion
 
II - If the AE meets [1 AND 2A2] for a DJ then the AE is classified as an IRR associated with the DJ and associated with DJ+1 that meets the 2A2 criterion
 
III - If the AE meets [3 AND 4B] for any DJ then the AE is classified as an IRR associated with all DJ that meet the 4B criterion.
 
IV- If the AE meets [3 AND 4A1] for a DJ then the AE is classified as an IRR associated with the DJ that meets the 4A1 criterion
 
V- If the AE meets [3 AND 4A2] for a DJ then the AE is classified as an IRR associated with the DJ and associated with DJ+1 that meets the 4A2 criterion

1	PT is included in the ‘IRRs SIGNS and SYMPTOMS’ list
2A1	
 
• AE onset date = date of infusion of study drug DJ AND
 
• AE timing related to study drug DJ (‘DURING’, ‘AFTER’) AND
 
• [AE timing related to study drug DJ+1 (‘BEFORE’) OR AE onset date < date of infusion of study drug DJ+1] AND
 
• AE outcome in (‘RECOVERED/RESOLVED’, ‘RECOVERED/RESOLVED WITH SEQUELAE’, ‘RECOVERING/RESOLVING’) AND
 
• AE end date – AE onset date ≤ 2
 

2A2	
 
• AE onset date = date of infusion of study drug DJ AND
 
• AE timing related to study drug DJ (‘DURING’, ‘AFTER’) AND
 
• AE timing related to study drug DJ+1 (‘DURING’, ‘AFTER’) AND
 
• AE outcome in (‘RECOVERED/RESOLVED’, ‘RECOVERED/RESOLVED WITH SEQUELAE’, ‘RECOVERING/RESOLVING’) AND
 
• AE end date – AE onset date ≤ 2
 

3	PT is included in the ‘IRRs CORE’ list
4A1	
 
• AE onset date = date of infusion of study drug DJ AND
 
• AE timing related to study drug DJ (‘DURING’, ‘AFTER’) AND
 
• [AE timing related to study drug DJ+1 (‘BEFORE’) OR AE onset date < date of infusion of study drug DJ+1]
 

4A2	
 
• AE onset date = date of infusion of study drug DJ AND
 
• AE timing related to study drug DJ (‘DURING’, ‘AFTER’) AND
 
• AE timing related to study drug DJ+1 (‘DURING’, ‘AFTER’)
 

4B	AE onset on the day after infusion of study drug D J
